An additional secondary outcome of interest is the cost required to deliver the enhanced implementation support. Through the EBQI process, we determined the enhanced condition sites will each have a site-level champion. This champion will be a local leader in WISE implementation. Champions will receive an additional 3 hours of training to equip them to serve in this role. Champions will be supported by external facilitators from the WISE staff. The facilitators will meet with each champion in person at least once per month. Related to estimating the costs of this strategy, facilitators will track their contacts with sites (See Facilitation Log). We will also request tracking of efforts by site champions. (See Champion Log). Finally, we will ask all teachers to report monthly on their use of lesson and enhanced support materials (See Teacher Material Report). Data will be collected either through a secure RedCap Server or using paper and pencil.

Our partnering Head Start agency has 12 sites with 38 classrooms. Classrooms will be randomized to participate in either the basic (i.e., control) or enhanced implementation of WISE. Sites are all within Pulaski County and have a similar demographic make-up of ECEs and families. All families served meet the federal guideline for poverty (e.g., an annual income of \$24,250 for a family of 4). All ECEs will receive basic implementation supports (6-hour training at beginning of school year and monthly newsletter). Those randomized to the enhanced condition will receive the additional package of implementation support strategies developed in Aim 2 on a schedule agreed upon by the EBQI panel (e.g., monthly). These will be delivered by the PI or the research assistant. For both groups, we will collect child data before and after implementation. This will provide us with a matched design to assess comparative effectiveness. For both groups, the 6-hour training will be conducted in collaboration with the USDA-funded Team Nutrition project at UAMS (IRB # 206442). Their exempt training evaluation protocol will be in place. We will extract records from their database specific to our UAMS Head Start attendees, link with other study records, and then de-identify data using our coded ID system.

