Aim 3. 38 classrooms from our partnering Head Start agency will be randomized to implement the basic WISE strategy used in previous studies or the enhanced WISE strategy developed in Aim 2. Because the program is now adopting the WISE curriculum in all agency classrooms, WISE lessons are a part of normal educational activities. As such, we request a waiver of consent for these observations. In addition, 10 educators will be randomly selected and invited to provide feedback on feasibility and acceptability through semi-structured, open-ended interviews twice during the school year. We are requesting waiver of consent for these interviews as they would be the only document identifying teachers as participants in interviews. We will collect verbal consent on our audio recording. Teachers, directors, and champions will be paid \$25 for the interviews as they will take place outside of center hours.

Additionally, to assess comparative impacts on children, we will record review Body Mass Index (BMI) and Food Frequency Questionnaire (FFQ) data from the agency records at the beginning and end of the school year. We will collect a Resonance Raman Spectroscopy (RRS) assessment from children at the beginning and end of the school year as well. RRS is an optical scan of the hand to assess carotenoid intake from fruits and vegetables. It has been used safely in prior studies with children aged 3 and older. We expect to collect this information from up to 820 children between the ages of 3 and 5.

Risks and Benefits

As in all research, there exists the potential risk to study participants is the potential for loss of confidentiality. Measures to protect the confidentiality of study participants will be implemented as described in the Data Handling and Recordkeeping section below. No physical risks related to participation in this study are foreseen. Some educators may experience discomfort as a result of answering questions that they consider personal in nature. This risk will be minimized by their ability to withdraw from the study

Study Title: Developing and Testing Implementation Strategies for Evidence-Based Obesity Prevention in Childcare
PI: [name]
Institution: University of Arkansas for Medical Sciences
Support: NIH K01 DK110141-01, Arkansas Biosciences Institute (FUNDED)
NIGMS COBRE Center for Childhood Obesity Prevention (FUNDED)
or to refuse to answer any question which makes them uncomfortable.

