Aim 3. We will complete rapid coding of the semi-structured interviews with the selected ECEs at each iteration. This coding will focus on identifying aspects of the implementation feasibility and acceptability. Two coders will complete initial content analysis independently and come together to resolve any differences. These data will be combined with the fidelity data collected and presented to the EBQI panel. Changes or improvements to the enhanced strategy will be driven by these findings and the feedback from the EBQI panel.

At the completion of the study, analyses of Implementation and Effectiveness data will examine the descriptive statistics and examine outliers. Multi-level models (MLM) will be

Study Title: Developing and Testing Implementation Strategies for Evidence-Based Obesity Prevention in Childcare

PI: [name]

Institution: University of Arkansas for Medical Sciences

Support: NIH K01 DK110141-01, Arkansas Biosciences Institute (FUNDED)

NIGMS COBRE Center for Childhood Obesity Prevention (FUNDED)

used to account for the dependence among repeated observations of the same teachers in the same classroom as well as children nested within classrooms. MLM refers to a class of statistical techniques developed to analyze multi-level data structures and appropriately model clustered designs. The models will include a fixed term for intervention (basic versus enhanced) and time. Random effects will be included for the correlation of children within classrooms and the correlation of observations within teacher. This analysis will allow for estimation of variance in child outcomes accounted for by implementation (i.e., level 2) effects.

Ethical Considerations

This study will be conducted in accordance with all applicable government regulations and University of Arkansas for Medical Sciences research policies and procedures. This protocol and any amendments will be submitted and approved by the UAMS Institutional Review Board (IRB) to conduct the study.

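### Aim 3 names no child-outcome contrast; with only arm and time in the model and complete data, the arm coefficient targets half the end-of-year difference

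*Combined protocol and SAP*

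**What the plan says.** The Aim 3 paragraphs of Data Analysis describe one multi-level model for both Implementation and Effectiveness data. Its fixed part reads: "The models will include a fixed term for intervention (basic versus enhanced) and time". Its random part reads: "Random effects will be included for the correlation of children within classrooms and the correlation of observations within teacher". The only child quantity it promises is a variance share: "This analysis will allow for estimation of variance in child outcomes accounted for by implementation (i.e., level 2) effects".

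The design text for Aim 3 (Study Design and Procedures) promises more than that. It says "For both groups, we will collect child data before and after implementation", followed by "This will provide us with a matched design to assess comparative effectiveness". The same section plans to compare program impact on children's diet between the two conditions and classes the child measures as secondary outcomes. On clusters it says "Our partnering Head Start agency has 12 sites with 38 classrooms", with classrooms randomized to basic or enhanced.

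Study Population (Aim 3) gives the timing. BMI and FFQ are "data from the agency records at the beginning and end of the school year". For the scan, "We will collect a Resonance Raman Spectroscopy (RRS) assessment from children at the beginning and end of the school year as well". Up to 820 children are expected.

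Nowhere do the documents give an arm-by-time term, a baseline covariate, a change score, or a statement of which coefficient is the child effect.

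**The concern.** The plan promises a comparison of arms on child outcomes and does not say which number answers it. The terms it lists do not give the natural answer. In a randomized two-wave design, the arm main effect in a model without an interaction is an average over both waves, and one of those waves precedes any difference in implementation support. Read as the effect, it understates the end-of-year difference and tests it with less power than the collected data allow.

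This pilot is meant to explore child effects ahead of a larger, definitive study, so a halved estimate could be carried into that planning. Several analyses with different targets also fit the same paragraph, which leaves the choice open until the data are seen.

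Fidelity is not affected by the halving. Its three observations all fall within the school year, so Fall fidelity is not a pre-implementation value.

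**Working it through.** The plan states no Aim 3 effect size, SD, ICC, power or sample-size calculation, so there is no figure of its own to reproduce.

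**1. What the listed coefficient targets.** The model is E[Y] = b0 + b1·arm + b2·time, with random intercepts. Let the arm difference be 0 at Fall (in expectation, by randomization) and d at Spring. With complete data at both waves, generalized least squares (GLS) gives b1 the mean of the two differences:

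b1 = (0 + d)/2 = 0.50·d

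Exact GLS gave 0.500 at every ICC and Fall–Spring correlation tried, with equal or unequal classroom sizes. Adding arm-by-time, or constraining both arms to a common Fall mean, gave 1.000·d.

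**2. Incomplete or extra Spring records** (assumed rates, random, equal by arm). With a classroom intercept only, the share equals Spring records/(Fall + Spring records). With a child intercept as well, it comes from exact GLS with 20 children per classroom, ICC 0.01–0.10 and correlation 0.5–0.7.

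| Spring records | No child effect | With child effect |
|---|---|---|
| 10% lost, not replaced | 0.9/1.9 = 0.474 | 0.457–0.463 |
| 20% lost, not replaced | 0.8/1.8 = 0.444 | 0.412–0.424 |
| 30% lost, not replaced | 0.7/1.7 = 0.412 | 0.367–0.382 |
| 20% lost, half replaced | 0.9/1.9 = 0.474 | 0.460–0.464 |
| 20% lost, fully replaced | 0.500 | 0.500 |
| 10% more than at Fall | 1.1/2.1 = 0.524 | 0.534–0.539 |

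The documents do not settle which row applies. BMI is required twice a year and study packets go out at enrollment, so late enrollees could enter.

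**3. Power, illustrative.** From the plan: g = 38 classrooms and m = 820/38 = 21.6 children each. Assumed: equal allocation, ICC 0.01–0.10, Fall–Spring correlation ρ 0.5–0.7, and 0–80% of classroom variance changing between waves. On classroom means, in units of the child-level SD:

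- V = ICC + (1 − ICC)/m; s = ICC × (1 − share changing); C = s + (ρ − s)/m
- Listed model: effect d/2, variance (V + C)/2 × 4/g, df g − 2
- Spring adjusted for classroom Fall mean: effect d, variance (V − C²/V) × 4/g × (1 + 1/(g − 4)), df g − 3
- Arm-by-time: effect d, variance 2(V − C) × 4/g, df g − 2

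Example with ICC 0.05, ρ 0.6, half of classroom variance changing, d = 0.30: V = 0.0940 and C = 0.0516.

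- Listed: 0.15/√0.00767 = 1.71, power 39%
- Adjusted: 0.30/√0.00711 = 3.56, power 93%
- Arm-by-time: 0.30/√0.00892 = 3.18, power 87%

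Over the assumed ranges at d = 0.30:

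| Share changing | Listed | Adjusted, minimum | Arm-by-time, minimum |
|---|---|---|---|
| 0% | 23–57% | 99% | 99% |
| 20% | 25–58% | 91% | 87% |
| 50% | 27–59% | 78% | 67% |
| 80% | 30–61% | 69% | 52% |

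The smallest like-for-like gain over the listed model is 38 points (adjusted) or 21 points (arm-by-time). At d = 0.20, power is 13–32% (listed), 38–97% (adjusted) and 27–95% (arm-by-time), with smallest gains of 21 and 10 points.

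**4. Stress cases at d = 0.30.**

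- No child present at both waves (C = s): listed 25–75%, adjusted 66–97% (smallest gain 21 points), arm-by-time about 45–88% (smallest gain about 3 points).
- Whole sites allocated 6:6 (assumed site variance 0.01–0.03, site-by-time variance 0.005–0.02): listed 13–32%, adjusted 36–93%.

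**5. Simulation** (38 classrooms of 22, correlation 0.6, ICC 0.01/0.05/0.10, d = 0.30). Mean estimates were 0.145–0.154 (listed), 0.295–0.302 (Fall-mean adjusted) and 0.297–0.302 (arm-by-time). With no effect, rejection rates at the 5% level were 4.4–5.4% (listed), 4.6–5.6% (adjusted) and 4.6–5.9% (arm-by-time on classroom means). Arm-by-time with only a classroom intercept and unlinked records ranged from 0.1% to 18.7%; by formula over correlation 0.5–0.7, the range is 0 to about 20%.

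**The case against.** The best defence is that the paragraph is a sketch. Listing what a model will include does not exclude an interaction, and a before-and-after, matched comparison in both groups suggests change between arms. That stands as a reading: nothing here proves the literal model would be run. It does not supply the missing term, because the word matched names no contrast.

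Second, if intervention were coded as switched on only after baseline, the same two terms would recover the full Spring difference. The plan's own gloss, basic versus enhanced, reads as an arm label. If the other coding is meant, one sentence would settle it.

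Third, a classroom random slope for time would move the share away from one half even with complete data (about 0.33 at an assumed slope variance of 0.02). No slope is listed, so the one-half result holds for the model as written.

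Fourth, these are secondary outcomes in a pilot, the main child hypothesis concerns fidelity, and its definitive test is deferred. This lowers the weight, but the arm comparison is still planned.

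Fifth, the power figures rest on assumptions, and gains shrink with small effects: at 0.10 SD the smallest are about 5 points (adjusted) and 2–3 points (arm-by-time). That stands. The halving itself depends on no assumed ICC, correlation or effect size.

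**Conclusion.** The concern holds and should be fixed. The omission is certain. The halving is exact for the model as listed, given complete data, randomized classrooms and an arm indicator. Among the incomplete-data cases examined, the share falls below half when Spring losses are not fully replaced and rises above it when Spring records outnumber Fall records. A chance Fall imbalance would also pass into the coefficient at half its size.

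The power loss is real in every scenario examined, but its size is illustrative. Type I error for the listed arm coefficient is not inflated. The consequence is confined to BMI, FFQ and RRS.

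**What to change.** Add to Data Analysis, Aim 3, wording such as:

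> For each child outcome (BMI, FFQ, RRS), the effect is the difference at Spring, enhanced minus basic, estimated with the child's Fall value as a covariate or by an arm-by-time model with a common baseline mean. A classroom random effect is included and, where a child's two records can be linked by coded ID, a child random effect.

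BMI and FFQ are to come from an anonymous record review. If those records stay unlinked, adjust for the classroom Fall mean or use the arm-by-time contrast; both need only classroom and wave on each record. With arm-by-time, also include a classroom-by-wave random effect or analyse classroom means, because a classroom intercept alone does not hold the error rate.

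Specify fidelity separately, as the arm difference at each wave and averaged over waves.

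The cost is a few sentences and no new measurements. An IRB amendment may be needed only if coded linkage of agency records is chosen. The plain arm-by-time contrast has less power than Fall adjustment, so Fall adjustment is the better default.

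### The Aim 3 model for child outcomes names no arm-by-time contrast, no child effect and no classroom-by-time effect, so its arm effect is either diluted or, if arm-by-time is added, carries an unreliable standard error

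*Combined protocol and SAP*

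**What the plan says.** All references are to the Combined protocol and SAP.

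- **Data Analysis, Aim 3.** Multilevel models are "used to account for the dependence among repeated observations of the same teachers in the same classroom as well as children nested within classrooms". Repetition is mentioned for teachers; children appear only as members of classrooms. On fixed effects: "The models will include a fixed term for intervention (basic versus enhanced) and time". On random effects: "Random effects will be included for the correlation of children within classrooms and the correlation of observations within teacher". No interaction of arm with time is named.
- **Study Design and Procedures, Aim 3.** "Our partnering Head Start agency has 12 sites with 38 classrooms", and "Classrooms will be randomized to participate in either the basic (i.e., control) or enhanced implementation of WISE". For children: "For both groups, we will collect child data before and after implementation". The section calls this a matched design for comparing effectiveness. It also lists the child measures as secondary outcomes and describes the BMI and food-frequency record review as anonymous.
- **Study Population, Inclusion, and Exclusion, Aim 3.** The record review covers BMI and "Food Frequency Questionnaire (FFQ) data from the agency records at the beginning and end of the school year". The carotenoid scan (RRS) is taken at the same two times. On numbers: "We expect to collect this information from up to 820 children between the ages of 3 and 5".

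No intraclass correlation, within-child correlation, SE, alpha or power is given for any child outcome.

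**The concern.** The child question is whether children in enhanced classrooms differ from those in basic classrooms after a year, allowing for where they started. The listed terms do not answer it under either natural reading.

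Taken literally, the arm coefficient compares the arms averaged over both occasions. The first occasion precedes implementation, so any effect is diluted.

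If the analyst adds arm-by-time to the same two-record-per-child model, a constant classroom effect cancels from the Fall-to-Spring contrast. The contrast is then judged against pooled within-classroom variance, and two errors follow in opposite directions. Stable differences between children stay in the residual and inflate the SE. A shift shared by a whole classroom is treated as if it averaged out over its children, which deflates the SE for an effect randomised by classroom. The net error depends on quantities the documents do not give.

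At stake are the reported precision and false-positive rate for BMI, diet and carotenoids, which are meant to inform a later, definitive study.

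**Working it through.** There is no planned figure to reproduce, so the check compares SEs under stated assumptions.

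**Inputs from the documents.** 38 classrooms, up to 820 children, two occasions, randomisation by classroom. 820/38 = 21.6, so m = 21 is used.

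**Assumptions.** 19 classrooms per arm (the ratio is not stated); balanced data; total variance 1; one teacher effect per classroom, so that it adds nothing for child data; two-sided 5% test. Components are v_c (constant classroom), v_ct (classroom-by-time), v_child and v_e. The classroom ICC is v_c + v_ct, and r is the within-classroom Fall-Spring correlation of a child, so v_child = r(1 − ICC) and v_e = (1 − r)(1 − ICC).

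**1. Arm term as literally written.** With no difference in Fall and an effect d in Spring, the averaged arm effect is (0 + d)/2 = d/2. Its SE is close to right (simulated ratios of model to empirical SE about 0.96 to 1.02). The difficulty here is dilution.

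**2. Arm-by-time added, random effects unchanged.**

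- True SE = sqrt[(4/19)(v_ct + v_e/m)].
- Model SE = sqrt[(4/19) s²/m], where s² = [2(m − 1)v_child + (2m − 1)v_e + m·v_ct]/(2m − 1) is the pooled within-classroom mean square.

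*Case A: r = 0.9, ICC 0.03.* v_child = 0.873, v_e = 0.097.
- v_ct = 0.003: true SE = sqrt[0.2105 × (0.003 + 0.097/21)] = 0.040. s² = (34.92 + 3.977 + 0.063)/41 = 0.950, so model SE = 0.098. Ratio 2.44.
- v_ct = 0.006: 0.098 against 0.047. Ratio 2.07.

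*Case B: r = 0.5, ICC 0.10.* v_child = v_e = 0.45.
- v_ct = 0.04: true SE = sqrt[0.2105 × (0.04 + 0.45/21)] = 0.114. s² = (18 + 18.45 + 0.84)/41 = 0.910, so model SE = 0.096. Ratio 0.84, type I error 2[1 − Φ(1.96 × 0.84)] = 10%.
- v_ct = 0.05: 0.096 against 0.123. Ratio 0.78, type I error 13%.

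The cruder residual v_child + v_e + v_ct gives nearly the same answer: 2.1 to 2.5 times too wide in A; 15 to 20% too narrow in B, with type I error 9 to 12%.

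**3. Sensitivity** (ratio of model SE to true SE, v_c held at 0.03):

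| v_ct | r = 0.9 | r = 0.5 |
|---|---|---|
| 0 | 3.13 | 1.41 |
| 0.01 | 1.76 | 1.18 |
| 0.02 | 1.35 | 1.03 |
| 0.03 | 1.14 | 0.93 |
| 0.05 | 0.90 | 0.79 |

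The two errors cancel at v_ct of about 0.014 (r = 0.3), 0.023 (r = 0.5), 0.031 (r = 0.7) and 0.040 (r = 0.9).

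**4. Child intercept added but no classroom-by-time effect.** SE is about sqrt[(4/19)(v_ct + v_e)/m]. At r = 0.9, v_c = 0.03 and v_ct = 0.01, v_e = 0.096 and the ratio is sqrt[((0.01 + 0.096)/21)/(0.01 + 0.096/21)] = 0.59, a type I error of about 25%. A child effect alone is not sufficient.

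**5. Simulation under no effect** (250 data sets per row, REML fits for the first two analyses). Cells show mean model SE / empirical SD / rejections at |z| > 1.96.

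| Case | Arm-by-time, classroom intercept only | Spring on Fall, classroom intercept | Classroom-mean change |
|---|---|---|---|
| A, v_ct 0.003 | 0.098 / 0.038 / 0% | 0.038 / 0.036 / 3.6% | 0.040 / 0.038 / 5.6% |
| A, v_ct 0.006 | 0.098 / 0.047 / 0% | 0.046 / 0.044 / 4.0% | 0.047 / 0.047 / 6.0% |
| B, v_ct 0.04 | 0.095 / 0.116 / 11.2% | 0.101 / 0.100 / 4.8% | 0.114 / 0.116 / 6.4% |
| B, v_ct 0.05 | 0.096 / 0.121 / 13.6% | 0.105 / 0.102 / 3.2% | 0.121 / 0.121 / 5.6% |

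The last two analyses have SEs that match their actual variability.

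**The case against.** The strongest reply is that the plan is brief rather than wrong. One paragraph covers both fidelity and child outcomes. The time term is needed for the three fidelity waves in any case, and the plan places implementation effects at level 2. If classrooms are level 2, children can be level 1 with one record each, as a change score or a Spring value adjusted for Fall. The named classroom effect is then sufficient. This stands: a reader might infer that the random part fails for every pre-post analysis, and step 5 shows that it does not. But the plan names neither a change score nor a baseline covariate, while it does name a fixed time term and measures each child twice. An analyst following the text would not arrive at the sound analysis.

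A second reply is that no arm-by-time term is written, so its SE is not the plan's error. That is correct as far as it goes. What remains is the averaged arm effect, which does not fit a matched before-and-after comparison.

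Third, the sizes rest on assumptions. Giving a diet outcome with ICC 0.10 and r = 0.5 a v_ct of 0.01 to 0.02 instead of 0.04 to 0.05 gives ratios of 1.16 to 1.02, with no inflation of type I error. This also stands.

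Finally, these are secondary outcomes in a pilot, which limits the consequence.

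**Conclusion.** The point holds as a defect of specification with real consequences. Followed literally, the model halves any Spring effect. Extended in the obvious way, it gives an SE that is right only by coincidence of variance components.

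Under the assumptions above, the SE is about 2.1 to 2.4 times too large at r = 0.9 with v_ct of 0.003 to 0.006; the excess is 14% by 0.03 and has reversed by 0.05. It is about 16 to 22% too small, with type I error about 10 to 13%, at r = 0.5 with v_ct of 0.04 to 0.05.

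A reader might infer that BMI intervals will be far too wide and that diet and carotenoid tests will be anti-conservative. The documents support neither as fact: they give no within-child correlation or classroom-by-time variance for any outcome, and each direction reverses within plausible ranges. The change should be made, but the child outcomes' secondary status in a pilot keeps it below critical.

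**What to change.** In Data Analysis, Aim 3, add for BMI, FFQ and RRS: the arm effect is estimated from the Spring value, with the Fall value as covariate and a classroom random intercept, and is tested against between-classroom variation.

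An acceptable alternative is a two-record model with an explicit arm-by-time contrast and both child and classroom-by-time random effects added. It is a different estimator and usually less precise: in case B the empirical SD of the unadjusted change contrast was 0.116 to 0.121, against 0.100 to 0.102 with baseline adjustment.

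Also state that each child's Fall and Spring records are linked by a study code. This cannot be taken for granted. Study Design and Procedures, Aim 3, calls the BMI and FFQ review anonymous, and the coded ID there is described for staff training records. If linkage is not possible, analyse classroom-mean change, which needs only the classroom on each record.

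The cost is two or three sentences and a decision on linkage, which must be reconciled with the anonymous review. No new measurements are needed.

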Study Title: Developing and Testing Implementation Strategies for Evidence-Based Obesity Prevention in Childcare
PI: [name]
Institution: University of Arkansas for Medical Sciences
Support: NIH K01 DK110141-01, Arkansas Biosciences Institute (FUNDED)
NIGMS COBRE Center for Childhood Obesity Prevention (FUNDED)

Study Design and Procedures

Aim 1. We will use an explanatory sequential mixed methods design to understand barriers and facilitators specific to WISE implementation (quant→QUAL). Quantitative data gathered from monthly fidelity observations in previous implementations of WISE (i.e., quant) will be used to identify positive deviants and implementation failures for semi-structured interviews (i.e. QUAL). Concepts from the i-PARiHS framework will inform the interview guide. For example, we will ask educators about perceptions of the evidence-based practices that comprise WISE that impede or promote use of the innovation. We will also ask about contextual elements (e.g., values, organizational culture) that made the implementation of WISE easier or more difficult. Previous WISE educators (N = 44) with complete observational data will constitute the sample pool for semi-structured interviews. We will also interview directors from each of the 7 sites in previous WISE implementation to provide a multi-stakeholder perspective and expose potential organizational barriers and facilitators.

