Building on the Team Nutrition evaluation, we will also conduct surveys of teachers at the end of the school year in both treatment groups. These surveys will be a repeat assessment of measures included in the pre-training survey as well as addition of standardized measures of feasibility, appropriateness, and acceptability,⁹⁵ implementation leadership,⁹⁶ Organizational Readiness for Implementing Change,⁹⁷ the

Study Title: Developing and Testing Implementation Strategies for Evidence-Based Obesity Prevention in Childcare

PI: [name]

Institution: University of Arkansas for Medical Sciences

Support: NIH K01 DK110141-01, Arkansas Biosciences Institute (FUNDED)

NIGMS COBRE Center for Childhood Obesity Prevention (FUNDED)

About Feeding Children assessment,⁹⁸ and educator perceptions of the support they received.⁹⁹ For the enhanced group, we will also include questions on their use of aspects of the implementation strategy. Teachers will have to complete these surveys outside of their work schedule. Therefore, we will pay a \$25 incentive for every returned survey. The surveys are estimated to take 30 to 45 minutes. Given limited success with web-based surveys in this group, we will gather these surveys using paper and pencil.

We will complete fidelity observations three times per year: Fall (Sept – Oct), Winter (Jan – Feb), and Spring (March- April). See WISE Fidelity Form. We will train contract staff to conduct fidelity assessments using videos of previous WISE lessons and ensure 85% reliability is achieved. After the Fall and Winter assessments, we will determine which teachers are achieving fidelity. We will randomly select 5 ECEs to complete semi-structured interviews with study staff on aspects of feasibility and acceptability of the implementation. We will restrict our interviews to ECEs that are not achieving fidelity if 5 are in that category. After analysis of these interviews at each of the two iteration points, we will hold EBQI meetings to review the themes that emerged and the observed fidelity in the classrooms up to that point. With feedback from the EBQI panel, we will use this information to determine shifts needed to improve the enhanced strategy for the remainder of the school year.

Study Population, Inclusion, and Exclusion

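### The classroom random effect is worded for children only; if several teachers per classroom supply fidelity or report data, or one is replaced, the arm standard error would be too small

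*Combined protocol and SAP*

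**What the plan says.** Study Design and Procedures, Aim 3, names the unit of allocation: "Classrooms will be randomized to participate in either the basic (i.e., control) or enhanced implementation of WISE". The same section gives the numbers: "Our partnering Head Start agency has 12 sites with 38 classrooms". Study Population, Inclusion, and Exclusion, Aim 3, repeats it: "38 classrooms from our partnering Head Start agency will be randomized to implement the basic WISE strategy".

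Fidelity is scored on educators in Fall, Winter and Spring: "We will complete fidelity observations three times per year". Teacher-level data also come from monthly reports requested of all teachers and from end-of-year teacher surveys in both arms (Study Design and Procedures, Aim 3).

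Data Analysis, Aim 3, says that multilevel models will be "used to account for the dependence among repeated observations of the same teachers in the same classroom as well as children nested within classrooms". Arm and time are the fixed terms. On random effects the plan says: "Random effects will be included for the correlation of children within classrooms and the correlation of observations within teacher". The only term worded for repeated measures is thus "the correlation of observations within teacher". No site effect is mentioned. The documents do not state how many educators per classroom are observed or report, or what happens to the cluster when a teacher leaves mid-year.

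**The concern.** In a cluster-randomised comparison the standard error of the arm effect has to reflect variation between the allocated units. Here those are classrooms. The one classroom term in the plan is defined on children, and a fidelity or teacher-report data set has no child records for it to act on. What remains for those outcomes is a teacher term.

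Two teachers in one room share the children, the setting and the allocation. With only a teacher term they count as two independent units. A teacher who takes over mid-year also becomes a new independent unit, although the room and its allocation have not changed. For survey scales given only at the end of the year there is one record per teacher, so a teacher effect cannot be separated from residual error and the literal model has no clustering at all.

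A positive correlation within rooms would then make the interval for enhanced versus basic too narrow. This matters because a Hybrid Type 3 design exists chiefly to make that implementation comparison, and the protocol intends the pilot to lead to a larger study.

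**Working it through.** The documents give no sample size calculation, alpha, standard deviation or intraclass correlation, so there is no planned figure to reproduce.

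**Inputs from the documents:** 38 classrooms in 12 sites; three fidelity observations per year; fixed effects for arm and time; random effects as quoted.

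**Assumptions:** a two-sided 5% test; large-sample normal reference; the numbers of teachers, correlations, variance shares and replacement rates shown below.

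Throughout, R is the true standard error divided by the one the teacher-only model reports, and type I error = 2 × [1 − Φ(1.96 / R)].

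**1. One teacher per classroom all year.** With m teachers per classroom and correlation ρ between the mean scores of two teachers in the same room, R = √(1 + (m − 1)ρ). For m = 1, R = 1.00 and type I error is 5.0%, whatever ρ is.

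**2. Two teachers per classroom.** For m = 2, R = √(1 + ρ), and the reported standard error is too small by 1 − 1/R.

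| ρ (assumed) | R | SE too small by | Type I error |
|---|---|---|---|
| 0 | 1.00 | 0% | 5.0% |
| 0.1 | 1.05 | 5% | 6.2% |
| 0.2 | 1.10 | 9% | 7.4% |
| 0.3 | 1.14 | 12% | 8.6% |
| 0.5 | 1.22 | 18% | 11.0% |

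**3. Replacement only.** Take one observed teacher at a time, with a share q of classrooms changing teacher after the first of three observations, equally often in both arms. Set total variance to 1, residual variance to 0.5, classroom variance to c and teacher variance to t, with c + t = 0.5.

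- Unchanged classroom: both models give information 3 / (3 × 0.5 + 0.5) = 1.5.
- Changed classroom, teacher-only model: 1 / (0.5 + 0.5) + 2 / (2 × 0.5 + 0.5) = 1 + 1.333 = 2.333. The implied weights on the three observations are 1, 2/3 and 2/3.
- True variance of that weighted sum: c(7/3)² + t[1 + (4/3)²] + 0.5[1 + 4/9 + 4/9] = 5.444c + 2.778t + 0.944.

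So R² = [1.5(1 − q) + q(5.444c + 2.778t + 0.944)] / [1.5(1 − q) + 2.333q].

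- Low end, q = 0.10, c = 0.1, t = 0.4: R = √(1.610 / 1.583) = 1.008; type I error 5.2%.
- High end, q = 0.30, c = 0.5, t = 0: R = √(2.150 / 1.750) = 1.108; type I error 7.7%.

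**4. Limit of a classroom-level correction.** A two-arm comparison of 38 independently allocated classrooms has at most 38 − 2 = 36 degrees of freedom. If allocation in effect follows the 12 sites, it has at most 12 − 2 = 10. In that case a classroom-level standard error is itself too small by a factor √(1 + (38/12 − 1) × ICC) = √(1 + 2.17 × ICC). This is 1.05, 1.10 and 1.20 for assumed site ICCs of 0.05, 0.1 and 0.2, or type I error of 6.3%, 7.6% and 10.2%.

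**The case against.** The best defence is that teacher and classroom may coincide. The stated purpose of the model, dependence among observations of the same teachers in the same classroom, fits one continuing teacher per room. The maintenance outcome also follows teachers from Fall to Spring. If so, step 1 applies and nothing is wrong. This stands as far as it goes: a reader might infer from the wording that the standard error is definitely too small, but that needs several contributing teachers per room or turnover, and the documents state neither. They do not state the one-to-one arrangement either. The reports requested of all teachers and the teacher surveys leave room for co-teachers to enter separately, even if only one per room is observed for fidelity.

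Second, the sentence on random effects may mean that both terms go into every model. That reading is possible, but the classroom term is described through children, so an analyst following the text could properly leave it out for fidelity.

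Third, a reader might try to infer two educators per room from the earlier work, where the protocol says "Previous WISE educators (N = 44) with complete observational data will constitute the sample pool for semi-structured interviews". Over 7 sites that is 44/7 = 6.3 educators per site, against 38/12 = 3.2 classrooms per site now, a ratio of about 2. The documents do not support this. The protocol refers to earlier implementations in the plural, the pool is limited to educators with complete data, and the classroom counts of the 7 sites are not given. The ratio says nothing about who is scored in Aim 3.

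Fourth, Aim 3 is a pilot with no stated alpha or decision rule. That lowers the stakes of a nominal error rate, but the interval for the arm effect still has to be honest.

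**Conclusion.** The concern holds as a conditional gap in specification. Read literally, the fidelity and teacher-report models omit the unit that is randomised, and the plan does not state the one condition, a single teacher per classroom all year, that would make this harmless.

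The size depends wholly on assumptions: no inflation with one teacher and no turnover, or with zero correlation; type I error of about 6% to 11% with two teachers per room and correlation 0.1 to 0.5; and about 5% to 8% from replacement alone under the variance shares used. These figures are large-sample approximations and do not add the effect of few clusters.

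A reader might also infer that analysing by classroom would restore exactly 5%. The documents do not support that assurance. Study Design and Procedures, Aim 3, speaks of enhanced sites, each with a site-level champion, while no site term is planned. If the allocation in effect follows sites, classrooms are not the independent units either.

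**What to change.** In Data Analysis, Aim 3:

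- State how many educators per classroom are observed for fidelity and how many supply reports and surveys.
- For fidelity and teacher-report outcomes, include a classroom random effect with teacher nested in classroom. Drop the redundant level where the two coincide. For outcomes measured once per teacher, keep classroom.
- Keep a replacement teacher in the original classroom's cluster.
- Test the arm effect with Kenward-Roger or Satterthwaite degrees of freedom at the level of the allocated unit: at most about 36 if 38 classrooms are independently allocated, fewer if allocation in effect follows sites. State which applies, because the text on classroom randomisation and the text on enhanced sites must be reconciled first.

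The cost is a few sentences of analysis text and no new data collection, provided that fidelity and teacher-report records carry a classroom code. Randomising by classroom makes that likely, but the documents do not say so, and it should be confirmed. If teacher and classroom prove to be one-to-one, the model reduces to the one now described and nothing is lost.
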